4.9 Criteria for Holding, Discontinuing, or Modifying Study Drug

Management of suspected adverse drug reactions may require temporary treatment hold (until re-treatment criteria are met), reducing the dose of APX005M, or discontinuation of some or all investigational products as per Table 5. If a subject experiences several toxicities, the recommended dose modification should be based on the highest grade toxicity.

Up to two dose reductions are permitted for APX005M. There are no dose reductions for cabiralizumab or nivolumab.

Table 5: Criteria for Holding, Discontinuing, or Modifying Study Drug

	Toxicity	Grade	APX005M	Cabiralizumab	Nivolumab
Gastrointestinal AEs	Diarrhea/colitis	2-3	1 st occurrence: Hold	Hold	Hold
			2 nd occurrence: dose reduction [¥]	If not improving in 28 days with oral steroids: Discontinue	If not improving in 28 days with oral steroids: Discontinue
	Vomiting	4	Discontinue	Discontinue	Discontinue
Endocrine AEs	Hypophysitis/ Endocrinopathies	2-4	Hold only if clinically unstable	Hold only if clinically unstable	Hold only if clinically unstable

	Toxicity	Grade	APX005M	Cabirizumab	Nivolumab
	Hyperthyroidism	2-4	Hold only if clinically unstable	Hold only if clinically unstable	Hold only if clinically unstable
Hepatic AEs	Increased AST/ALT	3 (> 5 to ≤ 12x ULN) and bilirubin <2x ULN	Continue	Continue	Continue
		3 (> 12x ULN) for >14 days and not decreasing on steroids and bilirubin <2x ULN	Hold	Hold	Hold
		2-3 and total bilirubin >2x ULN or 3x baseline for patients with Gilbert's syndrome and no cholestasis or INR >1.5 not on warfarin	Discontinue	Discontinue	Discontinue
		4	Discontinue	Discontinue	Discontinue
Increased bilirubin	Increased bilirubin	2	Hold	Hold	Hold
		3	Hold If >48 hours with no cholestasis or > 5 days with cholestasis: Discontinue	If >48 hours with no cholestasis or > 5 days with cholestasis: Discontinue	If >48 hours with no cholestasis or > 5 days with cholestasis: Discontinue
		4	Discontinue	Discontinue	Discontinue

	Toxicity	Grade	APX005M	Cabiralizumab	Nivolumab
Skin AEs	Rash or other skin toxicity	3	Hold If not improving in 28 days: Discontinue	Hold If not improving in 28 days: Discontinue	Hold If not improving in 28 days: Discontinue
		4	Hold If not improving in 28 days: Discontinue	Hold If not improving in 28 days: Discontinue	Discontinue
Neurological AEs	Neurological Toxicity	2	Continue	Continue	Hold
		3	Hold	Hold	1 st occurrence: Hold 2 nd occurrence: Discontinue
		4	Hold	Hold	Discontinue
Infusion Reaction/ Cytokine Release Syndrome	Nivolumab infusion reaction	1-2	Administer additional premedication. Increase infusion time to 90 min	Administer additional premedication. Increase infusion time to 60 min	Administer additional premedication and increase the infusion time to 60 min
		3	Hold	Hold	Hold. Re-challenge with nivolumab must be discussed with study PI
		4	Discontinue	Discontinue	Discontinue
	Cabiralizumab infusion reaction	1-2	Administer additional premedication. Increase infusion time to 90 min	Administer additional premedication. Increase infusion time to 60 min	Already given
		3	Hold	Discontinue	Already given
		4	Discontinue	Discontinue	Discontinue

	APX005M infusion reaction/	1-2	Administer additional premedication. Increase infusion time to 90 min*	Already given	Already given
		3	Hold and dose reduce [¥] for next cycle	Already given	Already given
	cytokine release syndrome	4	Discontinue	Discontinue	Discontinue
Pulmonary AEs	Pneumonitis	2-3	1 st occurrence: Hold 2 nd occurrence or if not improving in 14 days: Discontinue	1 st occurrence: Hold 2 nd occurrence or if not improving in 14 days: Discontinue	1 st occurrence: Hold 2 nd occurrence or if not improving in 14 days: Discontinue
		4	Discontinue	Discontinue	Discontinue
Renal AEs	Creatinine Elevation	2-3	Hold If not improving in 21 days: Discontinue	Hold If not improving in 21 days: Discontinue	Hold If not improving in 21 days: Discontinue
		4	Discontinue	Discontinue	Discontinue
Systemic AEs	Fatigue	3	Hold. Consider dose reduction for next cycle	Hold	Hold

	Toxicity	Grade	APX005M	Cabiralizumab	Nivolumab	
Hematologic AEs	Neutropenia	4	Hold	Hold	Hold	
	Febrile Neutropenia	3-4	Hold	Hold	Hold	
	Thrombocytopenia	2-3	Hold	Continue	Continue	
		3 with significant bleeding or transfusion or 4	Hold. Dose reduction¥	Hold	Hold	
Ocular AEs	Periorbital edema	2-3	Continue	Hold at discretion of treating investigator	Continue	
		4	Continue	Discontinue	Continue	
	Uveitis	2	Hold If not improving in 28 days: Discontinue	Hold If not improving in 28 days: Discontinue	If not improving in 28 days: Discontinue	
		3-4	Discontinue	Discontinue	Discontinue	
Laboratory AEs	CK increase without clinical or laboratory evidence of myocarditis or myositis	4 (> 15 to ≤ 20 x ULN)	Continue	Hold until returns to ≤ 15 x ULN	Continue	
		4 (> 20 x ULN)	Resume once < 10 x ULN	Discontinue	Resume once < 10 x ULN	
Toxicity All Other Drug-Related		3 or Severe	Hold	Hold	Hold	
		4	Discontinue	Discontinue	Discontinue	

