4.7 Criteria to Resume Treatment with APX005M, Cabiralizumab and Nivolumab

Patients may resume treatment with APX005M, cabiralizumab and/or nivolumab when the drug-related AE resolves as noted in Section 4.8 and Section 4.9.

A new treatment cycle should be initiated only if all toxicities are \leq Grade 1 except:

- Grade 2 neuropathy lasting shorter than 28 days (hold nivolumab only)
- Grade 2 alopecia
- Grade 2 rash or other skin toxicity
- Grade 2 hypophysitis/endocrinopathies
- Grade 2 fatigue
- Grade 2-3 neutropenia/lymphopenia
- CK increase up to 15x ULN

- AST/ALT \leq 12x ULN for \leq 7 days with bilirubin $<$ 2x ULN

If a subject fails to meet these retreatment criteria then the treatment cycle should be skipped.

The PI can be contacted at any time if further clarification is needed.

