4.11 Treatment Discontinuation Criteria

Subjects **must** discontinue receiving investigational products for any of the following reasons:

- Withdrawal of informed consent (patient's decision to withdraw for any reason)
- Toxicity requiring discontinuation of all investigational products as outlined in the dose modification guidelines
- Any clinically significant AE, abnormal laboratory test results, or intercurrent illness which, in the opinion of the Investigator, indicates that continued participation in the study is not in the best interest of the patient
- Failure to recover from a disease or treatment-related AE to baseline or \leq Grade 1 within 12 weeks of last dose of investigational product (except Grade 2 alopecia and Grade 2 fatigue), unless the subject is benefiting from therapy and after discussion with and approval by the PI
- Failure to recover within 4 weeks of last dose of investigational product if AE is related to infusion reaction/cytokine release
- Inability to reduce corticosteroid to 10 mg or less of prednisone or equivalent per day within 12 weeks of last dose of investigational product
- Patients who are required to have prohibited concomitant medications
- Pregnancy
- Termination of the study by the Sponsor
- Loss of ability to freely provide consent through imprisonment or involuntary incarceration for treatment of a psychiatric or physical (e.g., infectious disease) illness
- Documented disease progression or clinical deterioration while receiving active study therapy
- Requirement for alternative therapy
- Non-compliance with study procedures, including use of prohibited medications
- Subject is lost to follow-up
- Death

For comprehensive discontinuation rules, refer to the Table 5 in Section 4.4. The PI can be contacted at any time if further clarification is needed.

Other treatment discontinuation not specifically listed in Table 5 (Section 4.4) may include:

- Any event that leads to delay in dosing lasting > 6 weeks from the previous dose requires discontinuation, with the following exceptions:
 - Dosing delays to manage drug-related adverse events are allowed for up to 12 weeks between doses. Prior to re-initiating treatment in a patient with a dosing delay lasting

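### Section 4.9 lets the highest-grade toxicity set the dose modification, but Table 5 actions are not ordered by grade, so the rule can select a less restrictive action than another applicable row

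*Combined protocol and SAP*

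**What the plan says.** Section 4.9 gives one rule for concurrent toxicities: "If a subject experiences several toxicities, the recommended dose modification should be based on the highest grade toxicity". It states no exception and no rule for equal grades. Table 5 follows, with a separate action for each drug.

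Several Grade 4 rows are mild for at least one drug. For CK at >15 to 20x ULN, APX005M and nivolumab continue and cabiralizumab is on "Hold until returns to ≤ 15 x ULN". For CK above 20x ULN, cabiralizumab stops, but APX005M and nivolumab are on "Resume once < 10 x ULN". The endocrine rows, which run to Grade 4, read "Hold only if clinically unstable". Some lower-grade rows are stricter. The AST/ALT row that begins "2-3 and total bilirubin >2x ULN or 3x baseline" stops all three drugs, as does Grade 3 uveitis.

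Two other sections bear on this:

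- Section 4.11 lists reasons for which subjects must stop, among them "Toxicity requiring discontinuation of all investigational products as outlined in the dose modification guidelines". It also says "For comprehensive discontinuation rules, refer to the Table 5 in Section 4.4", although Table 5 is in Section 4.9.
- Section 4.7 requires all toxicities to be Grade 1 or lower, with listed exceptions, before a new cycle: "If a subject fails to meet these retreatment criteria then the treatment cycle should be skipped".

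**The concern.** A highest-grade rule is safe only if a higher grade always carries an action at least as strict. Table 5 is not built that way. It sets actions by organ and by drug, because a Grade 4 enzyme rise and a Grade 3 neurological event do not carry the same risk. Ranking by grade alone can therefore pass over the row that protects the patient.

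At stake is what happens after recovery: whether a drug is stopped for good or restarted, and whether APX005M comes back at a reduced dose or at the same dose. The same patient could be handled differently depending on whether the 4.9 sentence or the individual Table 5 row is followed.

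**Working it through.** The plan states no figure on this point, so there is none to reproduce. The check sets the rows side by side.

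**Step 1. Is Table 5 ordered by grade across toxicities?** Listed below are the rows that include Grade 4 and do not immediately stop all three drugs, with the number of drugs not discontinued outright. The diarrhea/colitis and vomiting rows are left out because the table is broken there in the text available.

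- Hypophysitis/endocrinopathies 3; hyperthyroidism 3
- Rash 2; neurological 2
- Neutropenia 3; febrile neutropenia 3; thrombocytopenia 3
- Periorbital edema 2
- CK >15 to 20x ULN 3; CK >20x ULN 2

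The sum is 3+3+2+2+3+3+3+2+3+2 = 26 of 10 x 3 = 30 drug cells. Two rows stop all three drugs outright below Grade 4: Grade 2-3 AST/ALT with bilirubin above 2x ULN (or the Gilbert's or INR criterion), and Grade 3 uveitis. The table is therefore not ordered by grade. The count describes the table only; it does not measure risk to patients.

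**Step 2. Apply the 4.9 rule and compare it with the other applicable row.**

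| Concurrent toxicities | Action by highest grade | Action in the other row | Covered by the 4.11 all-drug stop? |
|---|---|---|---|
| A. Grade 2-3 AST/ALT with bilirubin >2x ULN; Grade 4 CK >20x ULN | APX005M and nivolumab may resume; cabiralizumab stops | All three stop | Yes |
| B. Second Grade 3 neurological toxicity; Grade 4 CK >15 to 20x ULN | Nivolumab continues | Nivolumab stops | No |
| C. Grade 3 thrombocytopenia with significant bleeding; Grade 4 CK >15 to 20x ULN | APX005M continues | APX005M held, then reduced | No |
| D. Grade 4 rash; Grade 4 neutropenia | No rule, because the grades are equal | Nivolumab: stop (rash) or hold (neutropenia) | No |

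**Step 3. Do other sections settle these cases?**

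- *Case A.* The 4.11 reason is mandatory and is not conditioned on other toxicities, whereas 4.9 speaks of a recommended modification that should be followed. The natural result is that all three drugs stop.
- *Cases B to D.* The 4.11 reason concerns toxicity that stops all investigational products. It does not reach the loss of one drug or a reduction of APX005M. The general pointer to Table 5 in 4.11 does not say which row prevails.
- *Section 4.7.* It delays dosing in every case. In B, neither Grade 3 neurological toxicity nor CK above 15x ULN is among its exceptions, so no cycle starts until both improve. It imposes no permanent stop and no dose reduction, so the difference appears at restart.
- *Infusion reactions.* These are largely settled elsewhere. Section 4.4.1.2 ends cabiralizumab for a Grade 3 or higher reaction, and 4.4.1.3 reduces APX005M after a Grade 3 reaction.

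**Step 4. Are DLT counts affected in B or C?** No, if the events fall in the 28-day window and are not clearly due to another cause. Grade 3 neurological toxicity is a DLT under item 4 of Section 3.1.2.1.1, and Grade 3 thrombocytopenia with clinically significant bleeding is one under item 3, whichever Table 5 row governs.

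**The case against.** The strongest case against the point is that the plan already protects the patient. Section 4.11 is mandatory for rows that stop all three drugs, and 4.7 blocks dosing until all toxicities have settled, with listed exceptions. The trial runs at a single institution, and both 4.7 and 4.11 let staff contact the PI for clarification. The investigator may also stop treatment for any clinically significant adverse event. Finally, the combinations look uncommon. Section 1.3.6.1.3.3 reports cabiralizumab enzyme rises without bilirubin elevation, and Section 1.4.3 describes enzyme elevations with normal bilirubin and INR. The same section does, however, record transient bilirubin rises in six APX005M subjects with liver metastases.

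Most of this stands. A reader might infer from case A that the protocol permits restart of APX005M and nivolumab after suspected liver injury. The documents do not support that, because 4.11 most naturally requires all three drugs to stop. One could answer that 4.11 is circular, since it refers back to the dose modification guidelines, which contain the highest-grade sentence. That reading is possible but strained.

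The objection does not dispose of cases B to D. There the remaining safeguards only delay dosing or rest on judgment, and the one explicit rule either points to the milder action or is silent.

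**Conclusion.** The point holds in a limited form. Taken literally, the 4.9 sentence can select a less restrictive action than another applicable row of Table 5. For rows that stop all three drugs, this is an inconsistency with 4.11, which most naturally prevails. For single-drug stops, APX005M dose reductions and equal grades, the plan does not say what to do.

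The size in patients cannot be given, because the documents report no rate for such toxicities occurring together; it is probably low. A reader might take the 14 Grade 4 CK events among 195 subjects in Section 1.3.6.1.3.3 and project a number of affected patients. That would not be sound: a CK rise alone creates no conflict, and the figure comes from a study of cabiralizumab without APX005M. Nor do the documents support an effect on DLT counts, ORR or the Simon two-stage design. No statistical result changes.

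This is a minor safety-wording correction and a cheap improvement. It rests on reading Table 5 as printed and on treating the mandatory wording of 4.11 as stronger than the recommendation in 4.9.

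**What to change.** Replace the sentence in Section 4.9 with:

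> When several toxicities are present, apply each applicable Table 5 row and, for each study drug, follow the most restrictive resulting action. Any row that requires discontinuation or dose reduction applies regardless of the grade of the other toxicities.

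This settles cases A to D, including ties, and brings 4.9 into line with 4.11. The second sentence keeps a hold in one row from displacing an APX005M reduction in another.

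The same amendment can correct the two pointers in 4.11 that place Table 5 in Section 4.4; it is in Section 4.9. That change is clerical.

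The cost is one sentence and two cross-references, with no extra visits, data or patients. The downside is possibly a few more discontinuations or dose reductions, all of which Table 5 already prescribes.

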4.10 Dose Reduction

Dose reduction for nivolumab and cabiralizumab are not permitted. Dose reduction for APX005M is permitted as below and as per Section 4.8 and Section 4.9.

¥APX005M Dose Reductions

Dose Level (mg/kg)	DL1 (0.03)	DL2 (0.1)	DL3 (0.3)
First Dose Reduction	0.01	0.06	0.2
Second Dose Reduction	Not applicable	0.03	0.1

4.11 Treatment Discontinuation Criteria

Subjects **must** discontinue receiving investigational products for any of the following reasons:

- Withdrawal of informed consent (patient's decision to withdraw for any reason)
- Toxicity requiring discontinuation of all investigational products as outlined in the dose modification guidelines
- Any clinically significant AE, abnormal laboratory test results, or intercurrent illness which, in the opinion of the Investigator, indicates that continued participation in the study is not in the best interest of the patient
- Failure to recover from a disease or treatment-related AE to baseline or \leq Grade 1 within 12 weeks of last dose of investigational product (except Grade 2 alopecia and Grade 2 fatigue), unless the subject is benefiting from therapy and after discussion with and approval by the PI
- Failure to recover within 4 weeks of last dose of investigational product if AE is related to infusion reaction/cytokine release
- Inability to reduce corticosteroid to 10 mg or less of prednisone or equivalent per day within 12 weeks of last dose of investigational product
- Patients who are required to have prohibited concomitant medications
- Pregnancy
- Termination of the study by the Sponsor
- Loss of ability to freely provide consent through imprisonment or involuntary incarceration for treatment of a psychiatric or physical (e.g., infectious disease) illness
- Documented disease progression or clinical deterioration while receiving active study therapy
- Requirement for alternative therapy
- Non-compliance with study procedures, including use of prohibited medications
- Subject is lost to follow-up
- Death

For comprehensive discontinuation rules, refer to the Table 5 in Section 4.4. The PI can be contacted at any time if further clarification is needed.

Other treatment discontinuation not specifically listed in Table 5 (Section 4.4) may include:

- Any event that leads to delay in dosing lasting > 6 weeks from the previous dose requires discontinuation, with the following exceptions:
 - Dosing delays to manage drug-related adverse events are allowed for up to 12 weeks between doses. Prior to re-initiating treatment in a patient with a dosing delay lasting

> 6 weeks from the previous dose, the PI must be consulted. Tumor assessments should continue as per-protocol even if dosing is delayed. Periodic study visits to assess safety and laboratory studies should also continue per protocol, or more frequently if clinically indicated during such dosing delays or per the Investigator's discretion.

- Dosing delays lasting > 6 weeks from the previous dose that occur for non-drug-related reasons may be allowed if approved by the PI. Prior to re-initiating treatment in a patient with a dosing delay lasting > 6 weeks, the PI must be consulted. Tumor assessments should continue per protocol every 8 weeks for the first 4 months and every 12 weeks (± 7 days) thereafter, even if dosing is delayed. Periodic study visits to assess safety and laboratory studies should also continue per-protocol or more frequently if clinically indicated during such dosing delays or per the Investigator's discretion.
- Any AE, laboratory abnormality, or intercurrent illness which, in the opinion of the Investigator, presents a substantial clinical risk to the patient with continued APX005M, cabiralizumab and/or nivolumab dosing.

All patients who discontinue study treatment should comply with protocol specified follow-up procedures as outlined in Section 5. The only exception to this requirement is when a patient withdraws consent for all study procedures or loses the ability to consent freely (i.e., is imprisoned or involuntarily incarcerated for the treatment of a psychiatric or physical illness).

If a patient was discontinued, the reason for discontinuation must be entered on the appropriate CRF. The date and reason for cessation of nivolumab, cabiralizumab, and APX005M will be documented, and the Investigator must make every effort to perform the End-of-Treatment Visits. Adverse event reporting will continue until 100 (± 7) days after the last dose of study drug or until initiation of subsequent anti-cancer therapy. Patients with ongoing SAEs will be followed until resolution or stabilization.

4.12 Infusion Delays and Missed Doses with Nivolumab, Cabiralizumab and APX005M

In case an infusion cannot be administered at a scheduled visit, it must be administered as soon as possible. If the delay is more than two days, the infusion at the originally scheduled visit will be considered a missed dose and the procedures at the next visit should be performed. There must be at least 12 days between study drug administration.

4.13 Treatment Beyond Progression

Accumulating evidence indicates a minority of patients treated with immunotherapy may derive clinical benefit despite initial evidence of progressive disease [60].

Patients treated with nivolumab, cabiralizumab and APX005M combination therapy will be permitted to continue treatment beyond initial RECIST v1.1 defined progressive disease, assessed by the Investigator, as long as the following criteria are met:

- Patients who will be treated beyond disease progression must review and sign an ICF before continuing on study drug
- The patient demonstrates investigator-assessed clinical benefit, and do not have rapid disease progression
- Tolerance of study drugs
- No decline in current ECOG performance status
- Treatment beyond progression will not delay an imminent intervention to prevent serious complications of disease progression (e.g., CNS metastases)
- Absence of signs, symptoms, and worsening laboratory values that would indicate rapid disease progression

A radiographic assessment/scan should be performed approximately 8 weeks (± 7 days) after initial Investigator-assessed progression to determine whether there has been a decrease in the tumor size or continued progressive disease. The assessment of clinical benefit should be balanced by clinical judgment as to whether the patient is clinically deteriorating and unlikely to receive any benefit from continued treatment with investigational products.

If the Investigator feels that any patient receiving nivolumab, cabiralizumab and APX005M will obtain clinical benefit by continuing treatment, the patient may remain on the trial and continue to receive monitoring according to the time and event schedules per protocol.

For the patients who continue nivolumab, cabiralizumab and APX005M study therapy beyond progression, further progression is defined as an additional 10% increase in tumor burden from time of initial progression. This includes an increase in the sum of diameters of all target lesions and/or the diameters of new measurable lesions compared to the time of initial progression. APX005M, cabiralizumab and nivolumab treatment should be discontinued permanently upon documentation of further progression.

